The success of intraligamentary injection versus inferior alveolar block in symptomatic mandibular molars with irreversible pulpitis: A randomized double-blind clinical trial.

In this randomized controlled clinical study, it is aimed to compare the success of buccal infiltration anesthesia + intraligamentary anesthesia and inferior alveolar block anesthesia + buccal infiltration anesthesia with acute symptomatic irreversible pulpitis in the mandibular molars.

It is not always possible to provide adequate anesthesia with only the inferior alveolar block anesthesia technique in patients with acute symptomatic irreversible pulpitis in the mandibular molar tooth. In order to complete endodontic procedures painlessly, clinicians mostly use supplementary anesthesia techniques such as buccal infiltrative, intraligamentary injection (ILI) or intrapulpal anesthesia.

The intraligamentary injection (a periodontal ligament injection) allows a local anesthetic solution to be injected into the cancellous bone adjacent to the tooth to be anaesthetized (6). Earlier reports indicate a success rate of 50–96% for supplemental IL injections achieving pulpal anesthesia in endodontic therapy (2,4,6–9). Studies using ILI as a primary anesthetic technique in mandibular molars²⁸⁻³⁰ generally yield 0.2-0.9 ml in the mesial and distal sulcus.

Malamed et al., performed ILI as a primary anesthesia technique in mandibular molar teeth and deposited 0.2 ml of anesthetic solution from the mesial and distal sulcus and achieved a 60% success rate.

This study is aimed a comparative evaluation between buccal infiltration anesthesia + intraligamentary anesthesia and inferior alveolar block anesthesia + buccal infiltration anesthesia methods for endodontic treatment of mandibular molars with acute symptomatic irreversible pulpitis that creates a challenging procedure for both the patient and the clinician.

Materials and Methods

This study protocol is planned as parallel arm, double blind, single-centered and randomized controlled clinical trial. The ethics committee approval required for this study was obtained from Republic of Turkey, Ministry of Health, Turkish Medicines and Medical Devices Agency (21-AKD-186). The participants of the study were informed about the study protocol, benefits, possible complications and participants' human rights and an informed consent form was signed. The participants were selected from among the patients who applied to the Cukurova University, Faculty of Dentistry, Endodontic Clinic, between the dates from January to March 2022.

Sample size determination were performed according to the results of the study conducted by Lin et al. It was calculated by taking into account under the assumption that the difference is 45%, the power is 80%, and the error rate is 5%, there should be 22 patients per group. The sample size was set to 25 patients per group for possible dropouts. For randomization, the block permutation method with a computer-aided block size of 10 was used.

A total of fifty patient with the diagnosis of symptomatic irreversible pulpitis in the mandibular first or second molar teeth were include this study. The following inclusion criteria were taken as a basis; systemically healthy patients (American Society of Anesthesiologists [ASA] Class I or II) and patients between the ages of 18-65. The patients were excluded from the study if there was a pregnancy or nursery; allergy or sensitivity history against to articaine, epinephrine or any other used medication/materials; taking any analgesic drug or medication that interfere pain response 12 h before treatment. Also, patients with pathologic periodontal pockets during probing, have any pathology in the areas that planned for injection and have periapical pathology were excluded when considering clinical diagnosis.

The history of intermittent or spontaneous pain, even after the thermal stimuli have been removed, were based on the diagnosis of SIP and supported by clinical and radiological evaluation. Patients who have teeth with deep dentin caries or restored with composite/amalgam were included to the study. Teeth with crown restorations or abutments were excluded. After determining the vitality of the pulp with positive response to electrical pulp testing (Parkell Inc. NY, USA), cold testing (Endo-Frost, Coltene-Roeko, Langenau,

Germany) were used to scale felt pain as “before the beginning of the treatment”. In radiological evaluation, it has been looked for evidence of caries or initial restoration and no change in periodontium.

In order to categorize patients' pain, the “Heft–Parker Visual Analogue Scale” (HP-VAS) was used (1) before the beginning of the treatment, (2) the beginning of the treatment, (3) after the perforation of the pulp, (4) during the extirpation of the pulp/instrumentation. HP-VAS is a 170 mm line without a value that written “no pain” in the head and “greatest pain I have ever experienced” at the end. This line was measured and divided into 4 categories; 0=no pain, ≤54 mm mild pain, 54-114 mm moderate pain, ≥114 mm severe pain.

Blinding and anesthesia procedures

The fifty patients that included in the study were randomly divided into 2 groups (n=25) in accordance with the randomization block. All anesthetic attempts were performed by an endodontist ([name]) who received the patients according to the group and teeth were isolated with rubber-dam to maintain the blindness. In all applications, 4% articaine hydrochloride with 1:100.000 epinephrine (Ultracaine® DS Forte ampule and cartridge, Sanofi Aventis, Germany) was used as anesthetic solution.

IANB group: A standard IANB injection was performed with a standard 27-G needle and dental injectors (Septodont, Saint-Maur-des-Fosses Cedex, France) using the traditional Halsted approach. After determining the injection site and performing aspiration, 1.8 mL of solution was injected at a rate of 1 mL/min to block the inferior alveolar nerve. The patient was questioned about lip numbness after fifteen minutes. If there was no numbness, patient was excluded. In the case of lip numbness was achieved, 1 mL of buccal infiltration anesthesia was applied to the buccal sulcus of the tooth. Then, tooth was isolated with rubber dam.

ILI group: Initially, 1 mL of buccal infiltration anesthesia was administered to the buccal sulcus of the tooth with a standard 27-G needle and dental injectors. After five minutes, ILI was performed using an ILI device (Sopira Citoject, Heraeus Kulzer GmbH Hanau, Germany) with needle of 30-G and 12 mm in length (Sopira Carpule). The needle tip was held obliquely to the long axis of the tooth and slowly entered to the periodontal ligament until feeling constant and uninterrupted back pressure. It was ensured that the needle was correctly placed in the periodontal area. Anesthetic solution was injected at 4 location (mesiobuccal, distobuccal,

mesiolingual and distolingual) in each tooth. Sophira device administers 0,06 mL anesthetic solution in each dosing unit. Thus, it was triggered 3 times for each location (0,18 mL) to achieve subsequent anesthesia. Totally, 0,72 mL solution were injected for each tooth. Then, tooth was isolated with rubber dam.

Endodontic intervention

Access cavity preparation was performed using a round bur by an endodontist ([name]) who is blinded about the participants' group. When the patient felt pain, the intervention was stopped and patient was allowed to mark on the HP-VAS. If the patient did not feel pain until the perforation of pulp chamber, it was recorded as no pain. After the perforation of pulp chamber, pulp was removed using a sharp excavator and HP-VAS was marked thirdly. Then, root canals were established using a size 10 K-file and working lengths were determined using an electronic apex locator. All root canals were prepared with Reciproc® (VDW, Munich, Germany) using an endomotor (VDW Gold; VDW, Munich, Germany). HP-VAS was marked again by patient to assign the felt pain during instrumentation. If this marking was no pain to mild pain, then the anesthesia was recorded as "successful". If this marking was moderate pain to severe pain, then the anesthesia was recorded as "failed". In the existence of pain, additional injections were administered in every stages of treatment belongs to intervention group (IANB or ILI or intrapulpal if pulpal perforation occurs). Root canal treatment was completed with routine irrigation and obturation procedures in a single visit.

Statistical Analysis

IBM SPSS Statistics Version 20.0 package program was used for statistical analysis of the data. Categorical measurements were summarized as numbers and percentages, and numerical measurements were summarized as mean and standard deviation. Chi-square test statistics were used to compare categorical measures between groups. The ShapiroWilk test was used to determine the assumption of normal distribution of the numerical measurements. Independent T test was used to compare the mean age of the groups. Generalized EstimatingEquations (GEE) method was used to examine the change in HP-VAS values during intervention and to determine the features that affect this change. Statistical significance level was taken as 0.05 in all tests.

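### Does the shared 54 mm limit of the mild and moderate HP-VAS bands leave anesthetic success undefined?

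*Combined protocol and SAP*

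**What the plan says.** Materials and Methods describes the pain scale and its four bands: "HP-VAS is a 170 mm line without a value", measured and then cut at "0=no pain, ≤54 mm mild pain, 54-114 mm moderate pain, ≥114 mm severe pain".

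The Endodontic intervention section turns the mark made for instrumentation into the outcome. "If this marking was no pain to mild pain, then the anesthesia was recorded as" a success; "If this marking was moderate pain to severe pain, then the anesthesia was recorded as" a failure.

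Statistical Analysis adds the test: "Chi-square test statistics were used to compare categorical measures between groups". It also plans a GEE model for the HP-VAS values over the treatment stages. It does not return to the band limits.

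The design figures, also in Materials and Methods, are "the difference is 45%, the power is 80%, and the error rate is 5%, there should be 22 patients per group", then "The sample size was set to 25 patients per group for possible dropouts".

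**The concern.** The number 54 is printed in two neighbouring bands. If the moderate range includes its endpoints, a mark of 54 mm is both mild and moderate, and therefore both a success and a failure. This is the one limit that matters for the outcome the trial sets out to compare, and no tie rule is written down.

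In an arm of 25, one patient is 1/25 = 4 percentage points of the success rate. If the result lay beside 0.05, the coding of one patient could decide significance, and a choice made after seeing the data could be questioned.

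**Working it through.** **Inputs.** From the documents: the bands, the success rule, the chi-square test, the 45-point difference and 25 per arm. Assumed, because the documents do not give them: recording to the whole millimetre, the chance q that a final mark is exactly 54 mm, and the success rates in the two arms.

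**1. The plan's own figure.** The band limits play no part in the sample size, but it shows the scale of effect the trial is built for. The two rates are not stated. Taking 35% and 80% as an example (mean 0.575), two-sided 5%, 80% power:

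- Uncorrected: n = [1.96·√(2·0.575·0.425) + 0.842·√(0.35·0.65 + 0.80·0.20)]² / 0.45² = 17.7.
- Continuity-corrected: (17.7/4)·[1 + √(1 + 4/(17.7·0.45))]² = 21.9, so 22 per group, as stated.

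**2. Which marks are ambiguous.** I classify every whole millimetre from 0 to 170 (171 values), reading the moderate range as including both endpoints, which is the reading least favourable to the plan:

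| Mark | Bands | Outcome |
|---|---|---|
| 0 mm | none and mild | success either way |
| 54 mm | mild and moderate | success or failure |
| 114 mm | moderate and severe | failure either way |

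Every other mark has exactly one band. So one value in 171 carries two outcomes. If 54 mm is given to either band alone, none does.

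**3. How often such a mark might occur.** With q = 1/171 = 0.0058 (marks uniform over the line) or q = 0.010 (an assumed higher value), the chance of at least one among 50 patients is 1 − (1 − q)⁵⁰ = 25% or 39%.

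**4. When one patient matters.** For success counts a and b out of 25 each, Pearson χ² = 50·[a(25 − b) − b(25 − a)]² / [25·25·(a + b)(50 − a − b)].

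| Counts | Pearson p | Yates p |
|---|---|---|
| 16 vs 9 | 0.048 | 0.090 |
| 15 vs 9 | 0.089 | 0.157 |
| 17 vs 9 | 0.024 | 0.048 |
| 20 vs 9 | 0.002 | 0.004 |
| 20 vs 10 | 0.004 | 0.009 |

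Both versions are shown because the plan says only chi-square. The conclusion moves only in tables next to 0.05, such as 16 vs 9 against 15 vs 9 (Pearson). Near the planned difference (20 vs 9 is 80% vs 36%, 44 points) one patient changes nothing.

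**5. Chance that the rule decides the result.** Each patient is a clear success, a 54 mm mark (probability q) or a clear failure. All outcomes at 25 per arm are enumerated, and I sum the probability of those where coding every 54 mm mark as success and coding every one as failure fall on opposite sides of 0.05. Ranges cover both values of q and both tests.

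| Assumed success rates | Chance of a different conclusion |
|---|---|
| 45 points apart (65/20, 80/35, 95/50%) | 0.6% to 2.6% |
| 20 to 30 points apart (80/50, 70/40, 60/30, 70/50, 80/55%) | 2.3% to 5.2% |

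If 54 mm marks could be coded patient by patient, even in opposite directions in the two arms, the upper bounds are about 3% and 6%.

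**The case for a change.** The strongest case for a change is that an outcome rule should not rest on inference. The moderate range also meets the severe band at 114 mm, so the endpoints are loosely written at both ends, and a reader who takes ranges as inclusive would code 54 mm as moderate and so as failure. On the assumptions above, at least one such mark has a 25% to 39% chance of occurring, and the repair costs one line.

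Part of this stands: the tie rule is not explicit, and the limit lies on the success cut. The contradiction, however, depends on reading the dash as inclusive, which the text does not say. The mild and severe bands carry explicit inclusive signs, the moderate band carries none, and the line is said to be cut into four categories, which implies that the categories do not overlap. On that reading moderate is whatever lies between the two signed limits. A repair would write down this same convention. Patients mark a line that shows no values, so they cannot steer towards or away from 54 mm, and a single rule used for everyone treats both arms alike.

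**Conclusion.** The shared limit is a notational slip in the band definition, and no change to the plan follows. The signed bands point to 54 mm as mild and therefore as success. An analyst would apply that convention without being told, and the opposite convention, used in both arms, would be equally fair.

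The choice between the two would alter the chi-square conclusion in roughly 1% to 3% of trials at the planned 45-point difference and about 2% to 5% at 20 to 30 points. These figures rest on an assumed 0.6% to 1.0% chance of a 54 mm mark, on assumed success rates and on 25 analysed patients per arm. Finer recording would lower the chance of a tie, and clustering of marks near 54 mm would raise it. The analysed arms may be smaller than 25, since patients in the block group without lip numbness are excluded, so the tables are illustrative. The limits at 0 and 114 mm never change success or failure, and a GEE model fitted to the millimetre values does not use the bands.

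### IANB patients without lip numbness are excluded after randomisation, and the ILI arm has no matching rule, so the success comparison is biased towards IANB whenever those patients would do worse

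*Combined protocol and SAP*

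**What the plan says.** The section on blinding and anaesthesia procedures puts allocation first: "The fifty patients that included in the study were randomly divided into 2 groups (n=25) in accordance with the randomization block". IANB patients then receive the block. "The patient was questioned about lip numbness after fifteen minutes", and "If there was no numbness, patient was excluded". Only those with a numb lip go on to buccal infiltration, rubber dam and treatment.

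ILI patients receive buccal infiltration and then the four-site injection. The nearest thing to a check is on delivery: back pressure is felt, and "It was ensured that the needle was correctly placed in the periodontal area". No patient response is tested, no exclusion is attached, and the patient goes to rubber dam.

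Under Endodontic intervention, success is decided at the instrumentation marking on the Heft–Parker scale (HP-VAS): "If this marking was no pain to mild pain, then the anesthesia was recorded as" successful; moderate or severe pain is failure.

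Under Statistical Analysis, "Chi-square test statistics were used to compare categorical measures between groups", and a GEE "method was used to examine the change in HP-VAS values during intervention". The section defines no analysis set. It has no rule for patients without numbness and no rule on replacing them. On sample size, Materials and Methods says "The sample size was set to 25 patients per group for possible dropouts", against a calculated 22.

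**The concern.** Absence of lip numbness is a response to the allocated injection. Removing those patients takes one form of block failure out of the IANB denominator, while ILI patients who respond poorly stay in theirs. The groups compared are then no longer the groups that were randomised.

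The opening section asks about the success of the two methods, not success given a numb lip. It also says that the block alone does not always give adequate anaesthesia, so block failure is part of the question.

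IANB success is overstated whenever non-numb patients would have succeeded less often than numb ones. That can hide a true ILI advantage or create a false IANB advantage. The GEE analysis has the same selection, because excluded patients have no intra-operative scores.

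**Working it through.** **The plan's own figure.** The plan gives a 45-point difference, 80% power, 5% error and 22 per group, but no base rates. Take 40% vs 85% as an assumption (mean 62.5%), two-sided:

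n = [1.96·√(2·0.625·0.375) + 0.842·√(0.40·0.60 + 0.85·0.15)]² / 0.45² = (1.342 + 0.510)² / 0.2025 ≈ 16.9.

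With continuity correction: (16.9/4)·[1 + √(1 + 4/(16.9·0.45))]² ≈ 21.1, rounded up to 22. Then 22/(1 − 0.12) = 25. The planned size is reproducible and is not in dispute.

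**Inputs for the bias**
- From the plan: 25 per arm, chi-square test, 5% level.
- Assumed, because the documents do not give them: *q*, the share of IANB patients without numbness (5, 10, 15, 20%); *s*, the success rate those patients would have had (0 as the upper bound on bias, and 30%); *p*, true IANB success among all randomised patients.

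**Formulas**
- Success among analysed IANB patients: c = (p − q·s)/(1 − q).
- Overstatement: c − p = q(p − s)/(1 − q). This is positive while s < p and zero at s = p.
- Example with p = 60%, q = 10%, s = 0: c = 0.60/0.90 = 66.7%.
- Rejection rates: exact binomial enumeration of the Pearson chi-square test without continuity correction, 25 ILI patients against 25 − X IANB patients, averaged over X ~ Binomial(25, q).

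**No true difference (60% in both arms)**

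| q | s | IANB success as analysed | Significant, favouring IANB | Any significant result |
|---|---|---|---|---|
| 0 | – | 60% | 3.0% | 6.0% |
| 5% | 0 | 63% | 4.3% | 5.9% |
| 10% | 0 | 67% | 7.0% | 7.8% |
| 15% | 0 | 71% | 11.3% | 11.6% |
| 20% | 0 | 75% | 18.3% | 18.4% |
| 5% | 30% | 61.6% | 3.4% | 5.5% |
| 10% | 30% | 63.3% | 4.3% | 5.9% |
| 15% | 30% | 65.3% | 5.6% | 6.7% |
| 20% | 30% | 67.5% | 7.5% | 8.2% |

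A fixed count gives the same picture. If 3 of 25 are excluded and s = 0, IANB is analysed at 15/22 = 68.2% in expectation, with 8.6% of results significantly favouring IANB and 0.5% favouring ILI.

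**True ILI advantage (40% vs 85%).** Power is 94% without exclusions. For q = 5/10/15/20% it falls to 91/87/81/74% at s = 0, or 93/91/90/87% at s = 30%.

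**Replacement.** If excluded patients are replaced up to 25 (60% vs 60%, s = 0), results favouring IANB are 4.8/7.9/13/21%. Replacement restores n but not the comparison.

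**Dropout allowance.** If the fifty are counted before exclusions, the chance of losing more than the 25 − 22 = 3 spare IANB patients is 3/24/53/77%.

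**The case against.** The strongest counter-case has four parts.

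1. **The size is assumed.** Neither q nor s is in the documents. Total error does not rise at q = 5%, or at q = 10% with s = 30%. With s = 50% it is 5.3–5.5% for every q from 5 to 20%. Seven of the eight power scenarios stay above the planned 80%. This stands: the direction is established, the amount is not.

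2. **s = 0 may be pessimistic.** The plan provides additional injections at every stage when there is pain, and success is scored only at instrumentation. A non-numb patient who continued would also have had the buccal infiltration. So s could exceed 30%, and s = 0 should be read as a bound.

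3. **The remedy has its own bias** if the target is pain at instrumentation. Counting non-numb patients as failures understates IANB by q·s. The two errors are equal at s = p/(2 − q), which for p = 60% is 0.6/1.9 ≈ 32% (q = 10%) or 0.6/1.8 ≈ 33% (q = 20%). Above that the failure rule is the more biased: with 60% in both arms, q = 20% and s = 50%, total rejection is 13.1%, against 5.5% under exclusion. This also stands. The rule answers a defined question in which a block that does not numb the lip has failed. It needs bounds alongside it for anyone whose question is pain at instrumentation.

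4. **The figures depend on the test.** The plan does not say whether a continuity correction applies. With one, null rejection is 2.6–4.1% throughout s = 30%. At s = 0 it is 2.9% and 4.0% for q = 5% and 10%. Corrected power at s = 0 drops further, from 89% to 84/78/71/62%.

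Two readings are also inferred: that all ILI patients are analysed, since no analysis set is defined, and when the fifty are counted. Neither changes the selection. None of this shows the exclusion to be balanced between arms or offset in the analysis.

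**Conclusion.** The concern holds, and the plan should be changed. As written, a post-randomisation, response-dependent exclusion in one arm determines who enters the main success comparison, and nothing in the Statistical Analysis section offsets it. The bias runs towards IANB whenever non-numb patients would have succeeded less often than the rest of the arm.

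Confidence is high in the defect and its direction, but not in its size. Across the assumed range (q of 5–20%, s of 0 or 30%, true success 60%), IANB success is overstated by 1.6 to 15 percentage points. The effect on the test runs from negligible to a sixfold rise in results favouring IANB (18.3/3.0 ≈ 6). It is nil if nobody lacks numbness or if s equals the arm's overall rate.

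**What to change.** In the Statistical Analysis section:

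- Make the primary success comparison all randomised patients in their allocated arm, with no lip numbness at fifteen minutes counted as anaesthetic failure. State that this defines failure of the block to numb the lip as part of the endpoint.
- Report the number without numbness, and whether the fifty are counted before or after exclusions or replacement.
- Present the numb-only comparison as a labelled secondary analysis.
- Add a sensitivity analysis that counts 30% and then all of the non-numb patients as successes, and report how many would have to be successes to change the conclusion. With three or fewer such patients, 30% is under one patient (0.3 × 3 = 0.9), so the tipping-point count and the all-successes bound carry the weight.
- State that the GEE analysis lacks intra-operative HP-VAS scores for these patients and is therefore conditional on numbness in the IANB arm.

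The cost is a few sentences. No extra patients are needed, and only the analysis rule changes, not clinical management. Reported IANB success will be lower, and IANB gains a route to failure that ILI lacks. If 30% of non-numb patients would have succeeded, a true 60% is reported as 0.60 − 0.10·0.30 = 57% at q = 10%, or 0.60 − 0.20·0.30 = 54% at q = 20%. Results favouring ILI are then 4.9% and 7.6% against 3.0%, and total rejection is 6.7% and 8.7% against 6.0%. That is why the sensitivity analysis belongs with the rule.

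### Success is scored only on the instrumentation mark although additional injections are given at every stage, so moderate or severe pain at access or pulp removal can still be recorded as success

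*Combined protocol and SAP*

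**What the plan says.** The opening section states the aim: "it is aimed to compare the success of buccal infiltration anesthesia + intraligamentary anesthesia and inferior alveolar block anesthesia + buccal infiltration anesthesia".

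The HP-VAS paragraph of Materials and Methods lists four marks. The first is made before treatment and the second at its start; the last two are "3) after the perforation of the pulp, (4) during the extirpation of the pulp/instrumentation".

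Under Endodontic intervention the order of events is:

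- During access: "When the patient felt pain, the intervention was stopped and patient was allowed to mark on the HP-VAS" (mark 2).
- After perforation, the pulp is removed with an excavator and the third mark is made.
- After canal preparation: "HP-VAS was marked again by patient to assign the felt pain during instrumentation" (mark 4).
- The next sentence is the success rule: "If this marking was no pain to mild pain, then the anesthesia was recorded as" successful. Moderate or severe pain on the same mark is a failure.
- Then: "In the existence of pain, additional injections were administered in every stages of treatment belongs to intervention group". These are IANB or ILI, or intrapulpal once the pulp is perforated.

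For the comparison, Statistical Analysis says "Chi-square test statistics were used to compare categorical measures between groups" and uses GEE for HP-VAS over the stages. Neither method is said to take additional injections into account.

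**The concern.** The success rule refers in the singular to the mark just described, the instrumentation mark. By then a patient in pain at access or pulp removal has already been given more anesthetic. Failure of the allocated combination can therefore be relabelled as success by the supplement that the failure triggered.

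At stake is the outcome that the trial exists to compare. Before perforation the supplement depends on the arm, so there is no reason to assume that failures are converted equally often in both arms. The chi-square test on recorded success cannot separate the effect of the technique from that of the supplements. HP-VAS values after a supplement also enter the GEE on the same footing as values before one.

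**Working it through.** **1. The plan's own figure.** The sample size rests on this statement: "under the assumption that the difference is 45%, the power is 80%, and the error rate is 5" per cent, giving 22 per group, raised to 25 for dropouts. No arm-specific rates are given. Take 40% and 85% as an assumption, with two-sided alpha 0.05 and pooled rate 0.625:

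- n = [1.96√(2×0.625×0.375) + 0.842√(0.40×0.60 + 0.85×0.15)]² / 0.45² = 16.9
- With continuity correction: (16.9/4)×[1 + √(1 + 4/(16.9×0.45))]² = 21.2, rounded up to 22.

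So 22 is reproduced, and the sample size itself is not in dispute.

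**2. Model.** In one arm, let p be the success rate when no failure is converted, and r the share of failures that end with a no/mild instrumentation mark. Then

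recorded success = p + (1 − p)r.

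This is never below p, so the rule can only raise the rate in each arm. With H the better arm and L the weaker, the bias in the difference is r_H(1 − p_H) − r_L(1 − p_L). The documents give neither r nor p. Everything below assumes values for both, and assumes that the 45-point difference refers to the allocated injections. If the cited study's definition already included supplements, the power figures do not apply.

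**3. Equal conversion, 40% vs 85%.** The difference becomes 45×(1 − r). Power is by exact binomial enumeration of the uncorrected Pearson chi-square.

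| r | Recorded rates | Difference (points) | Power, 25 per arm | Power, 22 per arm |
|---|---|---|---|---|
| 0 | 40% vs 85% | 45 | 0.941 | 0.895 |
| 0.25 | 55% vs 88.75% | 33.75 | 0.799 | 0.734 |
| 0.5 | 70% vs 92.5% | 22.5 | 0.573 | 0.508 |
| 0.8 | 88% vs 97% | 9 | 0.191 | 0.151 |

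For other 45-point pairs, from 25% vs 70% to 50% vs 95%, power at 25 per arm is 0.93–0.98 (r = 0), 0.73–0.91 (r = 0.25), 0.46–0.72 (r = 0.5) and 0.18–0.19 (r = 0.8). With a continuity-corrected test at 40% vs 85% and 25 per arm, power is 0.82 at r = 0.1 and 0.67 at r = 0.25.

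**4. Unequal conversion, 40% vs 85%.**

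- r = 0.2 (weaker arm) and 0.8 (stronger arm): 0.40 + 0.60×0.2 = 52%; 0.85 + 0.15×0.8 = 97%. The 45 points are kept.
- r = 0.8 and 0.2: 0.40 + 0.60×0.8 = 88%; 0.85 + 0.15×0.2 = 88%. The difference is erased.
- r = 0.9 and 0.3: 94% and 89.5%. The sign is reversed.
- Exaggeration needs r_H/r_L above 0.60/0.15 = 4.0 at these rates.

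**5. No true difference, 50% in both arms, 25 per arm.**

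- r = 0.25 and 0.75: 62.5% vs 87.5%; chance of significance 0.563 (0.496 at 22 per arm).
- r = 0.4 and 0.6: 70% vs 80%; 0.135.
- No conversion: 0.065.

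**The case against.** - **The reference to the mark could mean every mark.** The text does not say so. If that was intended, it has to be stated, and the remedy is the same.
- **The sections disagree on where extirpation pain is recorded.** The HP-VAS paragraph places extirpation at mark 4, the scored mark, while Endodontic intervention has the third mark made with pulp removal. This stands, and the two must be reconciled. Until then, it is uncertain whether extirpation pain falls inside the scored mark. Mark 3 itself is outside the rule on either wording, and the access-stage problem is unaffected.
- **The plan already holds early information.** The described order is pain, stop, mark, so the mark made when access is stopped probably precedes any supplement, and the GEE uses all stages. An early contrast between arms can therefore be obtained. This is a fair point, but it does not repair the success endpoint.
- **The sizes are assumed and some are stress cases.** Also true. A patient whose first moderate or severe mark is mark 4 cannot be converted, so r = 0.8 needs most failures to appear earlier and be relieved. The intrapulpal option is not specific to an arm, which may limit asymmetry. Near the planned 45 points, equal conversion and most unequal settings bias toward no difference. The misclassification itself needs no assumption about rates.

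**Conclusion.** The concern holds. As written, the rule records failed initial anesthesia as success whenever a later mark is no or mild pain, so it does not answer the comparison in the stated aim. It can only raise recorded success in each arm. The documents do not fix the direction of bias in the difference. Dilution is the likeliest result near the planned 45 points, but erasure, reversal or a spurious difference are all possible.

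Under the assumed 40% and 85%, with equal conversion and an uncorrected test, power at 25 per arm stays near 80% only up to about r = 0.25. With lower baselines, fewer patients or a continuity correction, that point comes sooner. The rule needs to be corrected before success rates are compared or interpreted.

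**What to change.** - **Main success outcome.** Define success as no or mild pain, at the plan's own threshold, at each of marks 2, 3 and 4. Any moderate or severe mark is a failure, whatever follows. The plan names no outcome as primary, so it should state that this one is.
- **Sensitivity analysis.** Count any additional injection as failure. This should not be the main rule, because additional injections follow any pain, including mild pain that the plan accepts as success.
- **Secondary outcome.** Keep the present rule, named as success including supplementary injections.
- **Reporting by arm.** Give the number, timing and type of additional injections, and the number of patients with a moderate or severe mark 2 or 3 but a no/mild mark 4. Interpret GEE values after a supplement as pain under the technique plus supplements.
- **Wording.** Reconcile the two sections on which mark covers extirpation.

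No change to the rescue treatment is proposed.

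**Cost.** The main rule needs only endpoint and analysis wording, since the three marks are already collected. The supplement-based analyses need a per-patient record that the document does not show to exist; with recruitment placed in January to March 2022, they may not be possible. If outcomes have been seen, the new definition must be labelled post hoc. Recorded success can only stay the same or fall. Marks made after a supplement for mild pain will still reflect that supplement, which only the sensitivity analysis addresses.
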